14.3.5. Publication Policy

The Sponsor encourages publication of results derived from the clinical research it sponsors. Publications include a paper in a peer reviewed medical journal, abstract submission with a poster or oral presentation at a scientific meeting, or making results public by some other means. The Sponsor will retain the right to review all material prior to presentation or submission for publication and neither institution(s) nor Study Co-chairs/Principal Investigator(s) are permitted to publish/present the results of the study, in part or in their entirety, without the written

authorization of the Sponsor. The review is aimed at protecting the Sponsor's pre-existing propriety information and commercial interests.

First Publication

The results of the entire multicenter study shall be presented in a first publication upon completion of the entire multicenter study (data lock), with authorship being determined by the Sponsor and Study Investigators using the criteria defined by the International Committee of Medical Journal Editors. At least two Sponsor representatives will also be included as coauthors on the first publication of the results of the entire multicenter study to allow recognition of the Sponsor's involvement in the design and execution of the study.

Subsequent Publications

Results from data subsets should not be published in advance of the first publication, and must make reference to it. Publications must include at least 2 Sponsor authors to allow recognition of the Sponsor's involvement.

In all publications, the study is to be identified as PUMA-NER-6203. The Study Principal Investigator(s) shall be free to publish or present, subject to the timing described in the Clinical Study Agreement.

17. APPENDICES

APPENDIX 1. SCHEDULE OF PROCEDURES

Table A1.1. Schedule of Study Procedures – Neratinib Monotherapy in the Extended Adjuvant Setting

Study Procedures	Screening ^a Days -28 to -1	Active Treatment ^b Cycle / Day (C/D)				Safety Follow-up Visit 28 Days After Last Dose
		C1/D1 (28-day cycle)	Colonoscopy 2	Post-second colonoscopy Visit 1-2-3	EOT Visit	
Study visit window in Days	0	-3 ^b	+/-3	Every 3 months ±10	±5	+5
Informed consent ^c	X					
Medical/Cancer history/Demography ^d	X					
ERBB2 status documentation ^e	X					
ECOG performance status	X					
Serum or urine β-hCG ^f	X	X				
Physical examination ^g	X	X	X	X	X	
Vital signs ^h	X	X				X
CBC plus differential ⁱ	X	X				
Serum chemistry ^j	X	X				
Liver function tests ^k	X	X		X		
INR	X					
ESR and CRP ^l		X	X			
MUGA or ECHO ^m	X					
ECG (12-lead)	X					
Colonoscopy ⁿ		X	X			
Fecal calprotectin and fecal elastase		X	X			
Concomitant medications or treatments ^o	X	X	X	X		
Neratinib administration ^p		Continuous once-daily dosing (pill count at each visit)				
Loperamide administration ^q		Loperamide dosing during C1	As needed			
Adverse events ^r		X	X-----X		X	

Abbreviations: β-hCG=beta-human chorionic gonadotropin; ALP=alkaline phosphatase; ALT=alanine aminotransferase; AST=aspartate aminotransferase; BUN=blood urea nitrogen; C=cycle; CBC=complete blood count; CRP = C-reactive protein; D=day; ECG= electrocardiogram; ECHO=echocardiogram; ECOG=Eastern Collaborative Oncology Group; eCRF=electronic case report form; EOT = end of treatment; ESR = erythrocyte sedimentation rate; FISH =

fluorescence in situ hybridization ; Hb=hemoglobin; Hct=hematocrit; IHC=immunohistochemistry; INR = International Normalized Ratio; LFT=liver function test; LDH=lactate dehydrogenase; MUGA=multiple-gated acquisition scan; NP=nurse practitioner; PA=physician's assistant; RBC=red blood cell; SAE=serious adverse event; TEAE=treatment-emergent adverse event; WBC=white blood cell.

- ^a Screening procedures and enrollment may occur on one day, however, enrollment must not be done before all screening procedures have been completed and results confirming eligibility have been reviewed.
- ^b Cycle 1 is defined as 28 days. The EOT Visit will be performed as soon as possible, but no later than 5 business days after the last dose and before start of new anticancer regimen. If patient discontinues neratinib for reasons of toxicity or disease progression, all activities indicated for the EOT Visit should be conducted within 5 business days of last dose of neratinib. All visit dates are calculated from the date of first dose. If a visit occurs before or after a scheduled visit date, the next visit is still expected to occur on the date initially calculated for this visit, and is not shifted due to an earlier or later prior visit.
- ^c Informed consent must be obtained before any protocol required assessments are performed. Certain procedures done prior to informed consent as part of the standard work-up are acceptable, as long as they have been performed within 28 days from the date of enrollment. Acceptable procedures are: CBC (with differential), serum chemistry, MUGA/ECHO, and ECGs. When obtaining the patient's informed consent, the Investigator must review with the patient the Patient Instructions for the management of diarrhea and the Patient Diary for the patient's daily recording of neratinib dose, any adverse reactions, number of loose stools and use of loperamide and/or other antidiarrheals (adverse reactions, stools, and antidiarrheals are to be documented only for the first cycle [28 days]). Both the patient and the Investigator must sign the patient instructions for the management of diarrhea. Copies of both documents are handed to the patient before she leaves the site with neratinib and loperamide on Cycle 1/Day 1. The Investigator must also complete and sign the Investigator Checklist by Cycle 1/Day 1.
- ^d Collect presence of chronic conditions and/or medical history of significance; include review of history of cardiac, pulmonary, and gastrointestinal disease including assessment of bowel movements experienced during the previous 28 days as well as those ongoing at the time of screening, any medical conditions that require medication, and therapies such as chemotherapy/biotherapy/immunotherapy.
- ^e Documentation of locally assessed ERBB2-amplified status by FISH (>2.2) or ERBB2 overexpression by IHC (3+) by a validated approved method must be confirmed.
- ^f For women of childbearing potential, serum or urine β -hCG test to be performed both at screening and repeated within 72 hours prior to Cycle 1/Day 1.
- ^g Physical examination may be delegated and performed by a properly trained NP, PA or equivalent. During treatment, brief symptom-guided physical examinations including worsening of medical history conditions will be done approximately every 3 months. As per [Section 12.3](#) beginning with Cycle 3 through the end of the study and during visits scheduled per standard of care, only SAEs will be reported.
- ^h Vital signs will be measured after resting in a seated position for 5 minutes, prior to dosing, and will include: blood pressure (systolic and diastolic; mmHg), resting heart rate (beats per minute), body temperature (°C), respiration rate, weight (kg), height (screening only).
- ⁱ CBC to include Hct, Hb, platelet count, RBC and WBC count plus differential. CBCs must be tested at screening and on Day 1 of Cycle 1 (-3 days), and as clinically indicated. The Cycle 1/Day 1 tests do not need to be performed, if the screening tests were done within 72 hours of enrollment.
- ^j Serum chemistry tests include sodium, potassium, chloride, calcium, magnesium, BUN or urea, serum creatinine, albumin, LDH, phosphorus, and glucose (non-fasting). The Cycle 1/Day 1 tests do not need to be performed, if the screening tests were done within 72 hours of enrollment.
- ^k LFTs must include total bilirubin, ALT, ALP, and AST. LFTs must be tested at screening, on Day 1 of Cycle 1, and approximately every 3 months, and as clinically indicated. Visits for LFT testing should be aligned with CBC testing and other routine study visits when possible. LFTs should also be tested in patients experiencing Grade 3 or higher diarrhea or any signs or symptoms of hepatotoxicity, such as worsening of fatigue, nausea, vomiting, right upper quadrant pain or tenderness, fever, rash or eosinophilia. During the evaluation of potential hepatotoxicity, bilirubin should be fractionated and prothrombin time should be measured. Also, liver imaging should be obtained for patients with any signs or symptoms of hepatotoxicity and/or Grade 3 or higher LFT elevations, or as clinically indicated. Refer to the guidelines for the management of LFT changes in the main section of the protocol.

¹ ESR and CRP must be collected at the time of the Baseline colonoscopy or prior to initiation of neratinib in Cycle 1 and at the time of the second study colonoscopy procedure after the first 28-day cycle, i.e., Day 1 of Cycle 2 (+ 5 days). If Screening is to be performed within 72 hours of enrollment and the first colonoscopy, ESR and CRP testing may be performed at the time of screening.

^m During trial participation, ECHO or MUGA will be performed at Screening, and as clinically indicated. It is strongly recommended to use the same method of measurement for the same patient throughout the duration of the study.

ⁿ Colonoscopy will be performed after eligibility has been confirmed, but prior to administration of the first dose of neratinib on Day 1 of Cycle 1, Andon Day 30 (\pm 3 days). Oral medications, including the morning dose of neratinib, will be withheld on the day of the colonoscopy as per local standard of care. In addition, biopsies will be collected as described in [Section 8.2.2](#).

^o Concomitant medications and concomitant nonpharmacological treatments/therapies are recorded at screening from 28 days before signing of the informed consent form, on Day 1 of Cycle 1, on the day before and day of the second study colonoscopy procedure, and on Day 1 of Cycle 3.

^p Neratinib is to be self-administered as per instructions in [Section 6.1](#).

^q Loperamide is to be self-administered as per instructions in [Section 6.4.2](#). Patients are asked to document administration of neratinib and loperamide in a diary on a daily basis during the first cycle (28 days) of the study, and to return this diary to the site at appropriate visit. Individual patient dosing compliance should be reviewed by study site staff. Investigators must ensure that patients have loperamide on hand when starting to take neratinib. Neratinib will be dispensed directly by the study sites on or before Cycle 1/Day 1 and during subsequent visits as needed. Loperamide is the recommended standard therapy to treat diarrhea in this study. If alternative antidiarrheal medication is used, the reason must be documented in the source documents. Acceptable reasons are non-tolerance of loperamide or lack of efficacy.

^r From the signing of the informed consent form through 28 days of neratinib monotherapy following the second study colonoscopy procedure in patients with stage 1 to 3c breast cancer treated in the extended adjuvant setting, and in Cycle 2 in patients with mBC, TEAEs and SAEs will be monitored continuously and recorded in the eCRF. Patients must use the diary to document any episodes of diarrhea for the first cycle (28 days) of the study.

^r After the completion of Cycle 2 through 28 calendar days after the last administration of neratinib, only SAE data will be collected. Should an Investigator be made aware of any SAEs occurring any time after the reporting period that may be causally related to administration of neratinib, it should be promptly reported. All SAEs must be reported within 24 hours of awareness of the event using the SAE Report Form.

Table A1.2. Schedule of Study Procedures – Neratinib In Combination with Capecitabine in Metastatic Breast Cancer

Study Procedures	Screening ^b Days -28 to -1	Active Treatment ^a Cycle / Day (C/D)				Treatment Discontinuation 0-3 Days After Last Dose	Safety Follow-up Contact 28 Days After Last Dose
		C1/D1 (28-day)	C2/D1 (21-day)	Colonoscopy 2	C3+ (21-day) ^{q,r}		
Study visit window in Days	0	-3 ^b	±5		±5		±5
Informed consent ^c	X						
Medical/Cancer history/Demography ^d	X						
ERBB2 status documentation ^e	X						
ECOG performance status	X						
Serum or urine β-hCG ^f	X	X					
Physical examination	X	X ^g	X ^g		X ^g	X ^g	
Vital signs ^h	X	X	X		X	X	
CBC plus differential ⁱ	X	X			X	X	
Serum chemistry ^j	X	X			X	X	
Liver function tests ^k	X	X	X		X	X	
INR	X						
ESR and CRP ^l		X		X			
MUGA or ECHO ^m	X				X		
ECG (12-lead) ⁿ	X				X	X	
Colonoscopy ^o		X		X			
Fecal calprotein and fecal elastase		X		X			
Concomitant medications or treatments ^p	X	X	X	X	X		
Neratinib administration ^q		Continuous once-daily dosing (pill count at each visit)					
Capecitabine ^r			X		X		

Study Procedures	Screening ^b Days -28 to -1	Active Treatment ^a Cycle / Day (C/D)				Treatment Discontinuation 0-3 Days After Last Dose	Safety Follow-up Contact 28 Days After Last Dose
		C1/D1 (28-day)	C2/D1 (21-day)	Colonoscopy 2	C3+ (21-day) ^{q,r}		
Study visit window in Days	0	-3 ^b	±5		±5		±5
Loperamide administration ^q		Loperamide dosing during C1		As needed			
Adverse events ^{s,t}		X ^s	X ^t				X

Abbreviations: β-hCG=beta-human chorionic gonadotropin; ALP=alkaline phosphatase; ALT=alanine aminotransferase; AST=aspartate aminotransferase; BUN=blood urea nitrogen; C=cycle; CBC=complete blood count; CRP = C-reactive protein; D=day; ECG= electrocardiogram; ECHO=echocardiogram; ECOG=Eastern Collaborative Oncology Group; eCRF=electronic case report form; EOT = end of treatment; ESR = erythrocyte sedimentation rate; FISH= fluorescence in situ hybridization; Hb=hemoglobin; Hct=hematocrit; IHC=immunohistochemistry; INR = International Normalized Ratio; LFT=liver function test; LDH=lactate dehydrogenase; MUGA=multiple-gated acquisition scan; NP=nurse practitioner; PA=physician's assistant; RBC=red blood cell; SAE=serious adverse event; TEAE=treatment-emergent adverse event; WBC=white blood cell.

^a Cycle 1, neratinib monotherapy, is defined as 28 days. Cycle 2 and all subsequent cycles are defined as 21 days. Cycle 2 will begin after the completion of the second study colonoscopy procedure. The Treatment Discontinuation Visit will be performed as soon as possible, but no later than 3 business days after the last dose and before start of new anticancer regimen. All visit dates are calculated from the date of first dose of neratinib. If a visit occurs before or after a scheduled visit date, the next visit is still expected to occur on the date initially calculated for this visit, and is not shifted due to an earlier or later prior visit.

^b Screening procedures and enrollment may occur on one day, however, enrollment must not be done before all screening procedures have been completed and results confirming eligibility have been reviewed.

^c Informed consent must be obtained before any protocol required assessments are performed. Certain procedures done prior to informed consent as part of the standard work-up are acceptable, as long as they have been performed within 28 days from the date of enrollment. Acceptable procedures are: CBC (with differential), serum chemistry, MUGA/ECHO, and ECGs. When obtaining the patient's informed consent, the Investigator must review with the patient the Patient Instructions for the management of diarrhea and the Patient Diary for the patient's daily recording of neratinib dose, any adverse reactions, number of loose stools and use of loperamide and/or other antidiarrheals (adverse reactions, stools, and antidiarrheals are to be documented only for the first cycle [21 days]). Both the patient and the Investigator must sign the patient instructions for the management of diarrhea. Copies of both documents are handed to the patient before she leaves the site with neratinib and loperamide on Cycle 1/Day 1. The Investigator must also complete and sign the Investigator Checklist by Cycle 1/Day 1.

^d Collect presence of chronic conditions and/or medical history of significance (include review of history of cardiac, pulmonary, and gastrointestinal disease experienced during the previous 28 days as well as those ongoing at the time of screening, any medical conditions that require medication, and therapies such as chemotherapy/biotherapy/immunotherapy).

^e Documentation of locally assessed ERBB2-amplified status by FISH (>2.2) or ERBB2 overexpression by IHC (3+) by a validated approved method must be confirmed.

^f For women of childbearing potential, serum or urine β -hCG test to be performed both at screening and repeated within 72 hours prior to Cycle 1/Day 1.

^g Physical examination may be delegated and performed by a properly trained NP, PA or equivalent. During treatment, brief symptom-guided physical examinations including worsening of medical history conditions will be done on Day 1 of each cycle. As per [Section 12.3](#) beginning with Cycle 3 through the end of the study and during visits scheduled per standard of care, only SAEs will be reported.

^h Vital signs will be measured after resting in a seated position for 5 minutes, prior to dosing, and will include: blood pressure (systolic and diastolic; mmHg), resting heart rate (beats per minute), body temperature ($^{\circ}$ C), respiration rate, weight (kg), and height (screening only).

ⁱ CBC to include Hct, Hb, platelet count, RBC and WBC count plus differential. CBCs must be tested at screening and on Day 1 of Cycle 1 (-3 days), and as clinically indicated. Visits for CBC testing should be aligned with LFT testing and other routine study visits when possible. The Cycle 1/Day 1 tests do not need to be performed, if the screening tests were done within 72 hours of enrollment.

^j Serum chemistry tests include sodium, potassium, chloride, calcium, magnesium, BUN or urea, serum creatinine, albumin, LDH, phosphorus, and glucose (non-fasting). The Cycle 1/Day 1 tests do not need to be performed, if the screening tests were done within 72 hours of enrollment.

^k LFTs must include total bilirubin, ALT, ALP, and AST, as well as serum lipase and serum amylase. LFTs must be tested at screening, on Day 1 of each treatment cycle, and as clinically indicated. Visits for LFT testing should be aligned with CBC testing and other routine study visits when possible. LFTs should also be tested in patients experiencing Grade 3 or higher diarrhea or any signs or symptoms of hepatotoxicity, such as worsening of fatigue, nausea, vomiting, right upper quadrant pain or tenderness, fever, rash or eosinophilia. During the evaluation of potential hepatotoxicity, bilirubin should be fractionated and prothrombin time should be measured. Also, liver imaging should be obtained for patients with any signs or symptoms of hepatotoxicity and/or Grade 3 or higher LFT elevations, or as clinically indicated. Refer to the guidelines for the management of LFT changes in the main section of the protocol. Patients receiving neratinib and capecitabine on study should be monitored for signs or symptoms related to pancreatitis, including abdominal pain, especially epigastric pain radiating to the back and elevations in serum lipase and serum amylase. Severe pancreatitis can also be accompanied by ecchymotic discoloration of the perumbilical or flank regions, fever, hypotension, and hypoxemia. Serum lipase and (pancreatic) amylase should be measured at baseline and subsequently at any time if pancreatitis is suspected. If pancreatic enzymes are elevated, imaging should be performed in accordance with standard institutional protocols for investigation of acute pancreatitis.

^l ESR and CRP must be collected at the time of the Baseline colonoscopy or prior to initiation of neratinib in Cycle 1 and at the time of the second study colonoscopy procedure after the first 28-day cycle, ie, Day 1 of Cycle 2 (+ 5 days). If Screening is to be performed within 72 hours of enrollment and the first colonoscopy, ESR and CRP testing may be performed at the time of screening.

^m During trial participation, ECHO or MUGA will be performed at Screening, and should be repeated at Cycle 3/Day 1, Cycle 6/Day 1, Day 1 of every 6th subsequent cycle, as clinically indicated. It is strongly recommended to use the same method of measurement for the same patient throughout the duration of the study.

ⁿ ECGs should be performed at Screening, and should be repeated at Cycle 3/Day 1, Cycle 6/Day 1, every 6th subsequent cycle during the active treatment phase, and as clinically indicated. ECG should also be performed at Treatment Discontinuation if not done during the previous 12 weeks. Patients using drugs known to cause QT/QTc prolongation should be monitored closed with serial ECGs at the Investigator's discretion. Refer to [Appendix 6](#) for a summary of drugs known to have a risk of causing QT/QTc prolongation, potentially causing Torsade's de Pointes.

- ^o Colonoscopy will be performed after eligibility has been confirmed, but prior to administration of the first dose of neratinib on Day 1 of Cycle 1, and after the first 28-day cycle, i.e., Day 1 of Cycle 2 (+ 5 days). Oral medications, including the morning dose of neratinib on the day of the Day 1/Cycle 2 colonoscopy, will be withheld on the day of the colonoscopy as per local standard of care. In addition, biopsies will be collected as described in [Section 8.2.2](#).
- ^p Concomitant medications and concomitant nonpharmacological treatments/therapies are recorded at screening from 28 days before signing of the informed consent form, on Day 1 of Cycle 1, on Day 1 of Cycle 2, on the day before and day of the second study colonoscopy procedure, and on Day 1 of Cycle 3.
- ^q Loperamide is to be administered as per instructions in [Section 6.2](#). Patients are asked to document administration of neratinib and loperamide in a diary on a daily basis during the first cycle (28 days) of the study, and to return this diary to the site at appropriate visit. Individual patient dosing compliance should be reviewed by study site staff. Investigators must ensure that patients have loperamide on hand when starting to take neratinib. Neratinib will be dispensed directly by the study sites on or before Cycle 1/Day 1 and during subsequent visits as needed. Loperamide is the recommended standard therapy to treat diarrhea in this study. If alternative antidiarrheal medication is used, the reason must be documented in the source documents. Acceptable reasons are non-tolerance of loperamide or lack of efficacy.
- ^r Capecitabine therapy will begin following the completion of the second study colonoscopy procedure and will be administered on Day 1-14 of each cycle. **Note: capecitabine cannot be administered until after the second study colonoscopy procedure is completed.**
- ^s From the signing of the informed consent form through the end of Cycle 2 TEAEs and SAEs will be monitored continuously and recorded in the eCRF. Patients must use the diary to document any episodes of diarrhea for the first cycle (28 days) of the study.
- ^t After the completion of Cycle 2 through 28 calendar days after the last administration of neratinib, only SAE data will be collected. Should an Investigator be made aware of any SAEs occurring any time after the reporting period that may be causally related to administration of neratinib, it should be promptly reported. All SAEs must be reported within 24 hours of awareness of the event using the SAE Report Form.

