9.3. Treatment Discontinuation or End-of-Treatment Assessments

The EOT visit will occur within 5 business days of the last dose of neratinib monotherapy in patients with Stage 1 to 3c disease receiving extended adjuvant therapy and within 0-3 days after the last dose neratinib in patients with mBC. When a patient discontinues study treatment for reasons of toxicity, disease progression, or other reasons, an EOT visit will occur within 5 business days of last dose of neratinib.

The following will be performed in accordance with the Schedule of Procedures ([Appendix 1](#)):

- AE assessment; refer to [Section 13](#).
- Physical examination; refer to [Section 8.2.5](#).
- Vital signs, including weight. Refer to [Section 8.2.4](#).
- Disease recurrence as applicable. Refer to [Section 8.3.2](#).

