10. PATIENT WITHDRAWAL AND REPLACEMENT

10.1. Investigational Product Discontinuation

Patients **must** be discontinued from **investigational product** under the following circumstances listed below and in [Appendix 2](#), unless otherwise agreed with the Medical Monitor:

- If the patient requires more than 2 dose reductions of neratinib (see [Appendix 2](#))
- If neratinib is withheld due to an SAEs for >28 days. Patients who are clinically benefiting from therapy with neratinib may be resumed on therapy after 28 days if approved in advance by the Sponsor
- Disease recurrence
- Initiation of alternative anti-cancer therapy. Any concurrent chemotherapy, radiotherapy (including palliative radiotherapy), surgery related to cancer, anticancer immunotherapy, or other anticancer treatments including other investigational agents (see [Section 7.3](#)).
- Pregnancy (see [Section 13.4](#))
- Investigator request
- Patient request (i.e., withdrawal of consent for treatment)
- AEs/toxicity

Withdrawal due to AE should be distinguished from withdrawal due to other causes, and recorded on the appropriate AE page of CRF. If a patient withdraws due to toxicity, even if discontinuation is not otherwise required per protocol guidelines, the withdrawal should be classified as withdrawal due to AE.

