10.3. Procedures for Investigational Product Discontinuation/Study Withdrawal

When a patient is withdrawn from the study, the Investigator will notify the Sponsor. In all cases, the reason(s) for premature discontinuation/withdrawal, and the primary reason, must be recorded on the CRF. If a patient is prematurely withdrawn from the investigational product or the study for any reason, the Investigator must make every effort to perform the evaluations described for the EOT visit (performed within 5 days of the last dose of investigational product as appropriate). If a patient discontinues due to an AE, he/she should be strongly encouraged to undergo the EOT assessments and continue to be under medical supervision until symptoms cease or the condition becomes stable.

If a patient is lost to follow-up, or voluntarily withdraws from study participation, every effort should be made to determine why a patient is lost to follow-up or withdraws consent. This information, including the date, should also be recorded on the patient's conclusion of patient participation CRF.

All patients will remain on active study treatment until a cause of early treatment discontinuation occurs; these include disease progression, unacceptable toxicity, and withdrawal of consent ([Section 10](#)), or until study closure.

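### Stage 1-3c patients have no scheduled liver function test at the second colonoscopy or at end of treatment, which conflicts with Section 12.3 and differs from the metastatic schedule

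*Protocol*

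**What the plan says.** Table A1.1 in Appendix 1 of the protocol is the schedule for stage 1-3c patients. Its liver function row is marked at screening, at C1/D1 and in the column "Post-second colonoscopy Visit 1-2-3". The cells for Colonoscopy 2, EOT and Safety Follow-up are empty. Footnote k gives the rule: "LFTs must be tested at screening, on Day 1 of Cycle 1, and approximately every 3 months, and as clinically indicated". It then adds event-driven testing: "LFTs should also be tested in patients experiencing Grade 3 or higher diarrhea or any signs or symptoms of hepatotoxicity". Footnote b sets the calendar: "All visit dates are calculated from the date of first dose". It adds that an early or late visit does not move the next one.

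Section 9.3 makes up the EOT visit from adverse event assessment, physical examination, vital signs and disease recurrence. Early stops follow the same list. Section 9.3 says "When a patient discontinues study treatment for reasons of toxicity, disease progression, or other reasons, an EOT visit will occur within 5 business days", footnote b says "all activities indicated for the EOT Visit should be conducted within 5 business days of last dose of neratinib", and Section 10.3 says "the Investigator must make every effort to perform the evaluations described for the EOT visit". Section 9.4 uses the 28-day follow-up to collect SAEs.

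Three other places bear on this:

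- **Section 12.3** has laboratory results collected at screening, Cycle 1 and Cycle 2, summarizes abnormalities over that period, and keeps only liver tests at later visits. It does not limit the Cycle 2 results to metastatic patients. Footnote l of Table A1.1 treats the second colonoscopy as Day 1 of Cycle 2.
- **Table A1.2** (metastatic patients) marks liver tests at C2/D1 and at Treatment Discontinuation.
- **Section 8.2.3** puts blood volume for a one-year adjuvant completer at about 50 mL.

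**The concern.** Section 2.3.2 names hepatotoxicity among the reported effects of neratinib. The protocol's responses all start from a test result: repeat testing of important abnormal values (Section 8.2.3), the hold, reduce and stop rules of Table A2.4, and SAE reporting of potential Hy's Law cases. Under Table A1.1, an adjuvant patient takes the drug for about three months before the first scheduled on-treatment liver value. A patient who leaves early, for example at their own request or after recurrence (Section 10.1), may leave without one at the last dose.

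There is also a consistency problem. If the table is followed, the Cycle 1 and Cycle 2 summary promised in Section 12.3 would contain no scheduled on-treatment liver result for this cohort. If Section 12.3 is followed, it would. With about two sites, practice could differ by site.

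**Working it through.** **Plan's own figure.** Section 8.2.3 gives 15 mL at screening, 15 mL at C1/D1 and 5 mL about every three months up to one year, for a total of about 50 mL.

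- Three quarterly draws (the table's Visits 1-2-3): 15 + 15 + 3×5 = 45 mL.
- Four quarterly draws (months 3, 6, 9, 12): 15 + 15 + 4×5 = 50 mL.
- Three quarterly draws plus an ESR/CRP sample at Colonoscopy 2, assumed to be 5 mL: 15 + 15 + 3×5 + 5 = 50 mL.

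The stated total is reproduced in two ways, so it does not identify the schedule.

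**Inputs for the intervals.** Quarter = 365/4 = 91.25 days. Window ±10 days (Table A1.1). Anchor = first dose (footnote b). Second colonoscopy at Day 30 ± 3. EOT within 5 business days of the last dose (Section 9.3). I take the C1/D1 sample as drawn on the day of first dose.

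**First scheduled on-treatment test.** Visit 1 falls at Day 91, with a range of 91 − 10 = 81 to 91 + 10 = 101.

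**Longest interval before an early last dose.**

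- Stop just before Visit 1: about 91 days (81-101) since the pre-dose test.
- Stop between two quarterly visits: 91 days nominal. If the first visit is 10 days early and the next 10 days late, 91 + 10 + 10 = 111 days. The windows can add up in this way because footnote b does not shift the later visit.

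**After the change.** The first on-treatment test moves to Day 30 (27-33), about 91 − 30 = 61 days earlier. The last test falls within 5 business days of the last dose.

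**Is the blank EOT cell a table-layout error?** The vital signs row gives reason to ask: Table A1.1 leaves EOT blank there, while Section 9.3 lists vital signs at EOT. For liver tests, however, footnote k does not name EOT and Section 9.3 does not list them, so the text agrees with the blank cell.

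**Comparison with the metastatic schedule.** At C2/D1, metastatic patients have had neratinib alone for 28 days, as the adjuvant patients have. Table A1.2 marks a liver test at that point; Table A1.1 does not. The metastatic test may also serve as a baseline before capecitabine, so the comparison is supportive rather than decisive.

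**The case against.** The strongest reply is that the existing cover is broad. Footnote k allows testing whenever clinically indicated, and its triggers include common symptoms such as nausea, vomiting, fatigue and rash. Section 9 allows unscheduled procedures for safety at the investigator's discretion. The EOT visit includes an adverse event assessment and an examination, which should bring symptoms to light. This stands: most toxicity stops will be tested. It does not reach a rise without symptoms, because nothing would prompt the test.

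Second, no Cycle 2 is defined for stage 1-3c patients, and footnote l closely matches the metastatic footnote, so it may be carried-over wording. Section 12.3 also fits Table A1.2 imperfectly, since that table marks no blood count or chemistry at C2/D1. This weakens Section 12.3 as evidence of what was intended, but the conflict in the text remains and should be settled.

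Third, by EOT the drug has stopped, so only work-up and Hy's Law reporting remain of Table A2.4. That is true at EOT. At the second colonoscopy dosing continues, and the dose rules still apply.

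Three stronger readings are tempting, and the documents do not support them:

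- The column title might suggest that quarterly visits run from the second colonoscopy, giving longer gaps. Footnote b counts them from the first dose.
- The 50 mL figure might be taken to prove a month-12 draw. It is approximate, and the third sum above reaches it without one. Month 12 is suggested by the quarterly wording, no more.
- A patient who cannot complete the second colonoscopy might be assumed to take the last dose at about Day 30 with no on-treatment test. Section 10.2 says only that such a patient may have to leave the study, after discussion. It does not say that neratinib stops that day.

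**Conclusion.** The point holds as a scheduling gap and an internal inconsistency. For stage 1-3c patients, the table, its footnote and Section 9.3 agree that no liver test is scheduled at the second colonoscopy or at EOT. Section 12.3 reads otherwise for Cycle 2, and the metastatic schedule does otherwise at both points.

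The size is modest. The first scheduled on-treatment test is at about Day 91 (81-101), and the last scheduled test can precede an early last dose by up to about 111 days. These figures assume that the table is followed, that visits are counted from first dose, that no trigger is met and that the stop does not coincide with a quarterly visit. At most 5 patients are exposed on planned enrollment, and fewer if some are metastatic; replacements under Section 10.4 could add to this. The documents give no basis for a rate of missed liver events.

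A one-year completer need not have a gap, because testing about every three months can be read to include month 12. The primary endpoint is unaffected, and the liver outputs in SAP Sections 6.10 and 9.1 are descriptive. The change is worth making because it costs little and closes a small gap in individual safety monitoring.

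**What to change.** - In Table A1.1, mark liver function tests at Colonoscopy 2 and at EOT.
- In footnote k, add both time points and state that EOT includes early discontinuation. Let a quarterly test drawn at the EOT visit count as the EOT test.
- Add liver function tests to the list in Section 9.3.
- Update the approximate blood volume in Section 8.2.3 to match the final schedule, saying which draws it counts.

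The SAP can stay as it is, since it already lists laboratory data by collection time point.

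The cost is one or two draws of about 5 mL per stage 1-3c patient, at visits that already take place. At Colonoscopy 2 the liver tests can be added to the existing ESR/CRP draw. Taking 5 patients with two draws each at the plan's quarterly volume, the total is 5 × 2 × 5 = 50 mL across the trial, plus the document edits above.
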